4.10.16.2 Increased chance of pre-eclampsia

 $BP \ge 160/110mmHg$, Proteinuria $\ge 2g/24$ hrs, $\ge 2+$ dipstick and platelets $< 100\ 000\ \mu$ L, urine protein (mg/dL)/creatinine (mg/dL) ratio ≥ 0.3 , -elevated serum lactate dehydrogenase (LDH) level and activity, elevated serum transaminase levels-AST, ALT; persistence epigastric pain/headache/visual disturbances

4.10.16.3 Eclampsia Seizures

New onset of grand mal seizure activity or unexplained coma during pregnancy or postpartum period in a woman with hypertension in pregnancy or postpartum period.

4.10.16.4 HELLP syndrome

- 1. Hemolysis is associated with the following:
 - Total bilirubin >1.2 mg/dL
 - LDH >600 U/L
- 2. Elevated liver enzymes:
 - Aspartase aminotransferase (AST) >70 U/L
 - Alanine aminotransferase (ALT
 - LDH >600 U/L
- 3. A platelet count $< 100,000/\mu$ L

Sub-classification of HELLP based on the severity of thrombocytopenia:

- Class 1 Platelet count $>50,000/\mu L$
- Class 2 Platelet count $50,000-100,000/\mu L$
- Class 3 Platelet count 100,000-150,000/μL

4.10.17 Transmission linkages

Mothers who seroconvert after enrolments will have host/viral genetics factors determined transmission linkages assessment. Peripheral blood mononuclear cells will be collected for these HUU, HEI and HEU infants for NK cell phenotype and functional analysis.

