3.1 Main Objective

This study aims to establish a birth cohort to investigate the role of HIV and comorbidities on vertical HIV transmission, immune development and disease progression in children 0-2 years, HEU, HEI and HUU as the control group.

Objectives

A. All Mothers Regardless of HIV Status

- To determine the prevalence and incidence of coinfections (intestinal parasitic infections, HBV, HCV, CMV) malnutrition and non-communicable diseases (NCDs) (gestational diabetes mellitus, hypertensive disorders and CVD) risk factors over 24 months and relate all these comorbidities to:
 - a. Pregnancy outcome, infant growth, development, morbidity and mortality
 - b. Biomarkers of inflammation and immune activations

Infants

- 2. To determine vertically transmitted infections and incidence non-communicable diseases among infants.
- 3. To determine clinical and immunological profiles of HEI, HEU and HUU infants.

B. HIV+ Mothers: Chronic HIV infections

- 1. To determine vertical transmission rates of mothers with acute and chronic HIV infection on option B+
- 2. Determine any association(s) between different option B+ drug regimens, adverse pregnancy outcome, viral load suppression and CD4/CD8 counts on mothers and their infants

C. HIV+ Mothers; Acute HIV infections,

- 1. To determine the incidence of HIV in the postpartum period over the 2 years
- 2. To determine the viral set points, HIV suppression trends and biomarkers of immune activation
- 3. To determine the HIV and host genetic diversity and possible transmission linkages

Infants

To characterise natural killer cell phenotype and function longitudinally from cord blood at birth up to 2 years and relate to infant HIV acquisition , morbidity and mortality

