4.4 Inclusion Criteria

- Pregnant woman 18 years of age and above at 28-36 weeks gestation. The date of the last menstrual period (LMP) will be used to estimate gestational age.
- Planning to deliver at the study sites
- Able to give informed consent
 - Willing to be followed together with her baby from delivery up to two years
 - Willing to provide the required specimens

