4.9 Infants Procedures

From delivery infections, immunological profiles, co-infections patterns and trends, mortality will be determined and , feeding practices development , responses to standard vaccines, general health will be assessed. Types of specimen required and the test to be assayed are shown in **Tables 3 and 4**.

		Specimen Required							
Visits	Baby Status	Blood*	Stool**	Urine***	PBMCs****	1			
1	HIV+								
	HIV-								
2	HIV+								
	HIV-								
3	HIV+								
	HIV-								
4	HIV+								
	HIV-								
5	HIV+								
	HIV-								
6	HIV+								
	HIV-								
7	HIV+								
	HIV-								
8	HIV+								
	HIV-								
9	HIV+								
	HIV-								
10	HIV+								
	HIV-								
11	HIV+								
	HIV-								

Table 3: Types and total Volumes of Inf	fant Specimen Required
---	------------------------

*Generally blood samples will be tested for trend in immune profiles and coinfections.

**Stool samples will be tested for intestinal parasites

^{***} Urine for urinalysis

^{****}PBMC of infants born from mothers with acute HIV infection for NK cell phenotyping

Procedure	Specimen	1	2	3	4	5	6	7	8	9	10	
/Test	Required	Delivery	7-10 Day	6 wks	10 wks	14 wks	24 wks	36 wks	48 wks	72 wks	96 wks	
	(volume)		рр	pp V	рр	рр	рр	рр	рр	рр	рр	
CMV / HBV/ HCV	Sesement(1m)L)	• 🖌 (¥	Ť							~	1
HIV testing/all exposed infants	Plasma (2 mL)	~	1	1	~	1	1	1	1	1	1	
Parasites	Stool (5 grams)	1	1	~	1	1	1	1	1	1	1	
FBC/Differentials		~		✓		✓			1		✓	
Markers of immune activation, cytokines levels and trends	Blood,	1	1	1	1	1	1	1	1	*	1	
Urine dip stick	Urine (5 ml)		1						1		1	
Biochemistry	ALT, AST, albumin,		1	1		1			1		1	
	Sugar		1	✓		✓			1		✓	
			PMBC for int	fants born f	rom Mothers	with acute H	IV infections					
		HE	Infants only o	on First HI	V positive sar	nple, thereaft	er every 3 mor	nths				
T cell profile	Whole blood		1	1	~	~	1	~	1	~	1	
HIV RNA load*	Whole blood											1
HIV genetic diversity for Transmission	Whole blood										V]
linkages**												

Table 4: Type, Volume, intervals of collection and Purpose of Infant Specimens Required

All the tests will be done locally except for transmission linkages assay and NK cell phenotyping that will be done in South Africa.

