4.10.14 NK cell phenotypic and functional analysis

Phenotype (CD56+ dim and bright) and function on PBMCs.

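### The NK-cell objective starts at cord blood, but infants are selected for PBMC collection by a maternal event that usually comes after birth, and no step keeps cord PBMCs or secures an unexposed comparator.

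*Protocol*

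**What the plan says.** - **Objective.** Protocol 3.1, under part C on acute maternal HIV infection, sets the infant aim: "To characterise natural killer cell phenotype and function longitudinally from cord blood at birth up to 2 years", to be related to HIV acquisition, morbidity and mortality.
- **Material.** Section 4.10.14: "Phenotype (CD56+ dim and bright) and function on PBMCs".
- **Whose infants.** The footnote to Table 3 in 4.9 reads "PBMC of infants born from mothers with acute HIV infection for NK cell phenotyping". Section 4.10.17 opens with "Mothers who seroconvert after enrolments will have host/viral genetics factors determined transmission linkages assessment" and continues "Peripheral blood mononuclear cells will be collected for these HUU, HEI and HEU infants for NK cell phenotype and functional analysis".
- **Timing of maternal infection.** Entry under 4.4 is "Pregnant woman 18 years of age and above at 28-36 weeks gestation". Part C of 3.1 places the events it counts after delivery: "To determine the incidence of HIV in the postpartum period over the 2 years".
- **Cord blood.** Table 1 in 4.8 takes 50 mL at delivery from HIV-positive and HIV-negative mothers alike. Table 2 assigns cord blood to immune-activation and cytokine markers and to restriction factors. Section 4.10.1 describes serum from clotted samples and freezer storage, with no PBMC isolation step. The budget (4.10.23, Table 6) lists PBMCs for storage without saying from whom or from which visit.
- **Control group.** The main objective in 3.1 names HUU infants as the cohort's control group.

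**The concern.** The rule that selects infants for NK work depends on something that, for most of them, has not yet happened when the cord is cut. A site that follows the Table 3 footnote has no reason at delivery to isolate PBMCs from the cord blood of a woman who is still HIV-negative. If she seroconverts later, her infant joins the NK group without the birth value the objective starts from, and that value cannot be recovered.

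The comparison is also unsettled. Section 4.10.17 lists HUU, HEI and HEU infants, but its word for them points back to seroconverting mothers, and the footnote limits PBMCs to infants of mothers with acute infection. HUU infants of women who stay HIV-negative are therefore either included or excluded depending on which passage a site reads. At stake is the baseline of a named longitudinal objective and the group against which NK findings would be read.

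**Working it through.** **A figure the plan gives.** The NK objective has no sample size of its own. The nearest checkable figure is in 4.10.18: at least 417 infants left after 15% and 20% loss. Sequential retention gives 600 × 0.85 × 0.80 = 408, close to but below 417. This does not bear on the point, but the same loss rates are used below.

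**Inputs**
- 600 HIV-negative women (4.10.18).
- 3% incidence (4.10.18), with no time unit stated. Both readings are tried. The 3% is given there for the breastfeeding period; using it for late pregnancy as well is an assumption.
- Entry at 28-36 weeks (4.4). With birth at 40 weeks (assumed), this gives 12 to 4 weeks at risk before delivery.
- Follow-up to 96 weeks after birth (4.8).
- Loss of 15% in year 1 and 20% in year 2 (4.10.18), assumed even within each year.

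**Reading 1: 3% per year**
- Before birth: 600 × (1 − exp(−0.03 × w/52)). For w = 4, 8 and 12 weeks this is 1.4, 2.8 and 4.1.
- After birth, no loss: 600 × (1 − exp(−0.03 × 96/52)) = 32.3.
- After birth, with loss: person-years = 600 × (0.925 + 0.85 × 0.90 × 44/52) = 943, and 943 × 0.03 = 28.3.
- Share before birth, lowest: 1.38/(1.38 + 32.3) = 4.1%.
- Share before birth, middle: 2.76/(2.76 + 28.3) = 8.9%.
- Share before birth, highest: 4.14/(4.14 + 28.3) = 12.8%.

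**Reading 2: 3% cumulative, 600 × 0.03 = 18 events spread evenly over time**
- Before birth: 18 × 4/(4 + 96) = 0.7, up to 18 × 12/(12 + 96) = 2.0.
- After birth: 17.3 down to 16.
- Share before birth: 4% to 11%.

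These shares are upper limits on who could be recognised at delivery, because a seroconversion must also be detected by then and 4.8 gives a single study visit before delivery.

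**Passages side by side**

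| Question | 3.1 | Table 2 | Table 3 footnote | 4.10.17 |
|---|---|---|---|---|
| First NK sample | Cord blood | Cord blood not listed for NK work | Not stated | Not stated |
| Infants | Listed under acute infection; HUU is the control group of the cohort | – | Mothers with acute infection | HUU, HEI and HEU, referring back to seroconverters |

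None of these passages, nor 4.10.1, tells a site to keep cord PBMCs before the mother's later status is known.

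**The case against.** The strongest reply is that the raw material is there. Cord blood is drawn at every attended delivery and PBMC storage is budgeted without a subgroup limit, so a reader who infers that birth samples will not exist goes further than the documents allow. That stands: what is missing is an instruction to isolate and retain, not the blood.

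A reader might also infer that an unexposed group is impossible because every infant of a seroconverting mother is exposed. The documents do not support this. Section 4.10.17 names HUU infants, and an infant weaned before the mother's infection has neither in-utero nor breast-milk exposure. What remains is a conflict over who is sampled, with no NK comparator defined by source, number or age.

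Nor is the whole objective lost. It asks for NK findings to be related to HIV acquisition, morbidity and mortality. HEI against HEU infants within the seroconverter group, with samples after birth, still speaks to that. It does not itself demand an HUU contrast.

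Two cautions on the evidence also stand. The visit cells of Table 3 and the PBMC line of Table 4 show no legible marks in the text at hand, so the finding rests on the footnote and the narrative sections. The time unit of the 3% is not given, and a flat claim of fewer than one in ten fails at the upper end of the range.

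**Conclusion.** The point holds as a conflict between the NK objective and the sampling rules. Under either reading of the 3%, about 87% to 96% of qualifying maternal events come after the cord sample, leaving about 4% to 13% of target infants identifiable in time. This rests on 600 women at risk, birth at 40 weeks, a constant rate across late pregnancy and the postpartum period, and the protocol's own loss rates. The direction is not sensitive to these choices, because 4 to 12 weeks at risk before birth are set against 96 weeks after.

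Followed as written, the protocol would lose an unrecoverable birth value for most target infants and would leave the unexposed comparator open to interpretation. It does not make the birth value or the comparator impossible, and it does not affect the parent cohort. The matter should be corrected, and before deliveries begin if the birth value is wanted.

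**What to change.** 1. Reconcile 3.1, Table 2, the Table 3 footnote and 4.10.17 on whose infant PBMCs are kept and from which visit.
2. Restate the NK objective as running from the first infant sample after maternal seroconversion to 96 weeks, and name the comparison groups that will actually be sampled. The rewording costs nothing. If HUU or other comparison infants are added, they can attend scheduled visits, but each adds PBMC isolation and NK phenotyping, which 4.9 sends to South Africa.
3. If the birth value is to be kept, choose one of two statements:
   - Cord PBMCs are isolated and stored at delivery for infants of all women still HIV-negative. This means processing and storage for up to about 600 deliveries. NK assays can be limited to infants of women who later seroconvert and their chosen comparators. The added cost should appear in the budget.
   - The birth value is available only for infants of women who seroconvert before delivery, so about 1 to 4 infants. This adds little cost.

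A small random subsample of cord bloods would not repair the gap. As an illustration, storing 10% of deliveries would catch about 10% of the 16 to 32 later seroconverters, or 1.6 to 3.2 infants.

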4.10.17.1 Nucleic acid extraction and DNA Amplification

Total RNA was extracted from plasma using the NucliSENS isolation kit, based on the Boom *et al.*, method Briefly samples are lysed in a lysis buffer containing a chaotropic agent, guanidine thiocyanate. Cells, bacteria and viruses in the sample are lysed whilst proteins such as nucleases are denatured and inactivated. DNA and RNA bind to silica particles and everything else is washed following several washing steps with the wash buffer. Finally the nucleic acids are eluted from the silica particles using the elution buffer. Purified DNA will be stored at -80 for genotyping.*Taq* polymerase is a thermostable DNA polymerase named after the hot spring *Thermusaquaticus* bacterium. The primary PCR amplified an approximately 800-base pair (bp) fragment spanning the V3 and V4 region of the envelope (positions 6948–7537) on the HIV-HXB2 genome using HIV primers ENV 2 and NY3. Secondary or nested PCR amplified a 535-bp env gene fragment using a PCR Thermal cycler. Detection and quantification of secondary PCR amplicons were done using a 1% agarose gel electrophoresed together with a standard mass ladder and then stained with SYBR safe stain.

4.10.18 Sample Size Determination

Pocock's formula was used to determine sample size (n) required:

- $n = \frac{p_1(1-p_1)+p_2(1-p_2)(Z_{\alpha}-Z_{\beta})^2}{(p_1-p_2)^2}$
- Where p_1 and p_2 are proportion of success in population 1 and 2
- Z_{α} and Z_{β} are values of standard normal distribution
- α = Significance level
- $\beta = Power$

3% incidence rate has been assumed to factor in for the a high risk of vertical transmission in the breastfeeding period for the few anticipated acute HIV infection²³⁴.With the advent of cell phones the % loss to follow up may not be that bad and cannot be similar for the first and second year. Factored in the worst case scenario of a 15% and 20% loss to follow-up during the first and second year respectively, a minimum sample size required computed using **STATA** is 1200 (600 HIV+ and 600 HIV-) mothers. Assuming a 15% and 20% loss to follow up in the first and second year of the study respectively, should leave us with at least the 417 infants. The sample size has power to predict diseases outcomes of HEU children which must culminate in their improved management. The sample size has not factored in sample sizes of sub-studies linked to it in the **Appendices' Section 6.2**. Should there be sub-studies, they should fit within this parent protocol. These aim to address all the research gaps highlight throughout the literature review.

	a) HIV Chronic Infection		b) HIV Acute Infection	c) HIV Negative	Outcomes
Comorbidities	Treatment experienced Immune	Treatment naive Profiles for dif	ferent comorbidities c	ombinations	Prevalence and incidence of comorbidities, comorbidities trends relating comorbidities to
HBV HCV CMV					immunological profiles, pregnancy outcomes, vertical transmission of infections, patterns and
Anaemia Diabetes Nutritional Status					transmission linkages, infant/child growth and neurodevelopment
Hypertensive disorders					

Table 5: Pictorial Depiction of the Stratification

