1.0 Introduction

Use of effective prophylactic HAART in pregnancy has reduced vertical transmission rates of HIV down to about 1% from a high of more than 20% ^{13;14}. Thus the immediate benefit of HAART in pregnancy remains unquestionable, implying that most infants can now escape HIV infection. Consequently, the number of HEU infants is increasing, representing about 30% of all children born in most parts of SSA¹⁵. Despite these positive and impressive developments, HEU children have been shown to have substantially increased morbidity and mortality predominantly from infectious causes, particularly between 2 and 6 months of age, compared with their HIV unexposed uninfected (HUU) counterparts¹⁶⁻²¹. This observation is of great concern taking cognisance that over and above their ever increasing numbers, HEU alongside the HIV exposed and infected (HEI) infants, are now maturing into adults²², entailing that any problems specifically associated with these groups of children will be of major public health importance. So far it is not yet clear whether *in utero* exposure to HIV-1 and/or other co-morbidities including exposure to prophylactic HAART during pregnancy and/or infancy may predispose these infants to such infections.

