4.0 Methodology

4.1 Study Design

A prospective cohort study of 1200 pregnant women (600 HIV positive and 600 HIV negative). **Figure 1** below is the study flow diagram.

Viral load re-testing with be done for all Unsuppressed HIV load every 3 months

Figure 1: Study Flow Diagram

Key

*Pregnancy outcome include spontaneous abortions, birth defects, multiple births, low birth weights preterm infants, birth with prolonged hospitalization, birth requiring neonatal intensive care, maternal, perinatal and infant deaths.

**Coinfections include HBV, HCV, CMV and intestinal parasites

***NCD, non-communicable diseases (hypertensive disorders, malnutrition, diabetes)

**** For acute HIV infections ONLY

*****Adverse feotal outcomes include preterm birth (<37 weeks of gestation) low Apgar score<7, low birth weight, Fetal macrosomia, birth weight of more than 4,000 grams, birth defects, stillbirth (death of a fetus weighing \geq 500g or \geq 22 weeks gestation if weight is unavailable), early neonatal death (death between 0-6 days of life), neonatal death (death within the first 28 days of life), neonatal jaundice, infant death, intensive care unit admission, hospital admissions including documented local clinic treatments

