4.10.19 Ethics Statement

Ethical approval will be sought from the necessary institutional review boards, JREC and MRCZ. All study participants will give written informed consent. Permission for storage and future use of biological specimens, external shipping of specimens including genetic testing of blood samples will also be sought. This observational study involves minimal risks to both the mother and the baby hence one parental consent is sufficient. However, in case of death of the mother re-consenting will be done from either the father or any family member who shall have legal responsibility for the care and custody of the baby. In case of a child death, the mother will cease to continue participating in the study.

Permission has already been obtained from Harare City Health. The sensitivity of HIV infection and sexuality means that the mother's emotional response is a potential risk. Anxiety associated with sample testing and waiting for the results for HIV exposed children may also be experienced. Nevertheless the study will minimize such risks by providing the necessary education and counselling through the research nurses and where necessary, referring them to the appropriate clinics. Health education and counselling on pregnancy, delivery and childcare will be given to mothers on a continuous basis at every visit. The study will offer consultation and basic treatment to both the mother and child. Whenever necessary referrals will made through the clinic.

Each sub-study will apply for their respective ethical approvals to all the relevant ethical boards before they can access the data and/or specimens. However, some sub-studies may require separate consent forms should they entail collection of additional data from study participants. Those that rely on specimens and data collected through main study will need no additional informed consent.

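### Protocol section 4.10.18: the stated 15% and 20% losses leave about 408 mother-infant pairs per group (390 if additive), not the stated minimum of 417 infants

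*Protocol*

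**What the plan says.** Section 4.1 describes the design as "A prospective cohort study of 1200 pregnant women (600 HIV positive and 600 HIV negative"), and section 4.10.18 repeats the 1200, split equally by HIV status.

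Section 4.10.18 mentions the losses twice. The first time they are already built into the sample size: "Factored in the worst case scenario of a 15% and 20% loss to follow-up during the first and second year respectively". With them allowed for, 1200 mothers is presented as the smallest number that will do. The second time they are used to project what remains: "Assuming a 15% and 20% loss to follow up in the first and second year of the study respectively", the plan "should leave us with at least the 417 infants".

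The section does not say whether 417 is per group or overall, or whether it is the number required or the number expected. It also does not say whether the 20% applies to those still in follow-up after year 1 or to all enrolled. The sample-size formula is printed with symbols; the two proportions, the significance level and the power have no values.

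**The concern.** A retained number should follow from the enrolment and the losses stated beside it. Here it can be checked by one multiplication, and it does not agree. The protocol words 417 as a minimum under a worst case, so even a small shortfall makes the statement untrue as written.

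The figure is the section's only statement of how many children will remain at the end of follow-up. The main objective in section 3.1 concerns "disease progression in children 0-2 years, HEU, HEI and HUU as the control group", so these are the children on whom the two-year comparisons rest. A reader would take 417 as secured, and anyone planning a sub-study within the cohort could carry it forward.

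**Working it through.** **Inputs**, all from section 4.10.18: 600 mothers per group (1200 in total); 15% loss in year 1; 20% loss in year 2; stated remainder at least 417.

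**Step 1. Attempt to reproduce 417 from the stated losses.**

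| How the losses combine | Per group (from 600) | Total (from 1200) |
|---|---|---|
| Sequential: N × 0.85 × 0.80 = N × 0.68 | 510 after year 1, then 408 | 816 |
| Additive: N × (1 − 0.15 − 0.20) = N × 0.65 | 390 | 780 |

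None of the four results is 417.

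**Step 2. Which denominator does 417 have?** Suppose it were the total. Delivering 417 in total would take 417 / 0.68 = 613.2, so 614 mothers overall, or 417 / 0.65 = 641.5, so 642 overall. That is about half of 1200, so 1200 could not be the smallest sufficient enrolment. The per-group results of 408 and 390 are close to 417; the totals of 816 and 780 are not. The per-group reading is an inference, but it is the only one that fits the rest of the section.

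**Step 3. Size of the shortfall per group.**

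- Sequential: 417 − 408 = 9, and 9 / 417 = 2.2%.
- Additive: 417 − 390 = 27, and 27 / 417 = 6.5%.
- Two-year retention needed for 417: 417 / 600 = 69.5%, against 68% or 65% implied by the stated losses.
- Largest second-year loss that still leaves 417: 1 − 417 / 510 = 18.2% (sequential), or 1 − 0.15 − 0.695 = 15.5% (additive), against the stated 20%.

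**Step 4. Consequence for precision.** Standard errors, and differences detectable at fixed power, scale roughly with 1/√n whatever the outcome.

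- √(417 / 408) = 1.011, so about 1.1% larger at 408.
- √(417 / 390) = 1.034, so about 3.4% larger at 390.

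**Step 5. Where 417 might come from.** 600 / (1.20 × 1.20) = 416.7, which rounds to 417. This would be a required number multiplied up by 20% twice. The protocol does not describe that step and it does not use the stated 15%. With the stated rates, the same way of multiplying up gives 417 × 1.15 × 1.20 = 575, not 600. The origin of 417 therefore stays unknown. Even if this is the origin, multiplying up by 1 plus the loss rate does not preserve the required number. Dividing by the retention does, and gives 614 per group (sequential) or 642 (additive).

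**The case against.** **The denominator is not stated.** Read against all 1200 mothers, 816 or 780 remain, and a claim of at least 417 is literally true. This stands as a point about wording. It does not rescue the figure, because a total of 417 would need only 614 to 642 mothers and would contradict the status given to 1200.

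**The gap is small.** On the more natural sequential reading, 408 and 417 agree to within about 2%, and no analysis would change. This stands, and it limits the weight of the point. The figure is nevertheless worded as a minimum, and 408 is below it.

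**The units differ.** 417 counts infants and 408 counts mother-infant pairs. The key to Figure 1 says "Pregnancy outcome include spontaneous abortions, birth defects, multiple births" among other events and also lists stillbirth and infant death. Section 4.10.19 adds: "In case of a child death, the mother will cease to continue participating in the study". Multiple births raise the infant count; stillbirths and deaths lower it. The protocol gives no rates for these events and does not say whether deaths are inside the 15% and 20%. On the sequential reading, a net surplus of 9 infants over 408 pairs (9 / 408 = 2.2%) would close the gap. So a reader might infer that fewer than 417 infants will certainly remain, and the protocol does not support that. It supports only that 417 does not follow from the stated losses.

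**A stronger reading about power.** A reader might infer that the study is underpowered, or that the section's assertion of power for outcomes in HIV-exposed uninfected children is wrong. The protocol does not show this. Without values for the two proportions, the significance level and the power, neither the 600 per group nor the power sentence can be verified or refuted. That is a gap in reporting, separate from the arithmetic error.

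**A further reduction for infected infants.** One could also subtract HIV-infected infants using the transmission rate of about 1% in the Introduction. That rate is literature background, not a planning assumption, so no such figure is claimed here.

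**Conclusion.** The stated minimum of 417 infants does not follow from the section's own enrolment and losses. Per group, 408 mother-infant pairs remain if the losses are sequential, 9 short (2.2% of 417). If both losses refer to the original 600, 390 remain, 27 short (6.5%).

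This rests on two assumptions: that 417 is per group, which is inferred from the status of 1200, and that pairs stand in for infants, since nothing in the protocol allows a conversion.

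The error is real but small, about 1.1% on precision at 408. It calls for correcting a stated number. It does not call the design into question, and it is no ground for enlarging the study or for naming a new powered outcome.

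**What to change.** In section 4.10.18, label the retained number as per group, state how the two yearly losses combine, and count mother-infant pairs. Then:

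- If 417 was meant as the expected yield, replace it with about 408 pairs per group (816 in total), or 390 (780 in total) if both losses refer to the original 600.
- If 417 is the required number, say that 600 per group falls slightly short of it under the stated worst case, and describe precision at about 408 (or 390 if the losses are additive). Leave enrolment unchanged.

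The cost is a sentence or two and one multiplication, with no added participants, visits or data. The stated number becomes slightly less favourable, and in the second case the protocol acknowledges a small shortfall.
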